4.3.2 Secondary outcomes

Secondary outcomes will be collected at baseline, within the hospital 5 days post procedure, during early assessment at a prosthetic centre (if applicable) and at 4 monthly intervals post-randomisation (4, 8, 12-, 16-, 20- and 24-months post-randomisation). These will include quality of life, surgical and rehabilitation outcomes, as well as longer term social and functional outcomes. Where possible, data collection will rely on routinely collected information in clinical notes to minimise the requirement for active input from participants (Table 2). To ensure timely collection of data a visit window of +/- 21 days will apply to each visit timepoint.

Quality of life

• EQ-5D-5L data collected at baseline and 4, 8-, 12-, 16- and 20-months post randomisation as recorded by the participant via remote questionnaire.

Surgical outcomes

- Perioperative blood loss estimated using the pre and post operative Haemoglobin (14) (15), alongside details of any blood products used in the perioperative period, as documented in the patient medical record.
- Planned or unplanned high observation or intensive care admission, collected from the patient medical record.
- Procedural pain using a Visual Analog Scale (VAS). The VAS consists of a 100-milimeter line representing a continuous scale. The line is anchored at both ends with the verbal descriptors 'No pain' (=0) and 'Worst imaginable pain' (=100). The outcome will be recorded by the participant at daily intervals over the first 5 days post procedure and will require the research team to visit them daily to collect this.
- Within hospital complications. Specifically referring to major adverse cardiovascular events, renal impairment and delirium. This information will be collected from the patient medical record.
- Impaired wound healing (including wound infection), as recorded in the patient medical record and via patient reported data.
- Return to theatre for revision surgery at either the same or a higher level of amputation, as documented in the patient medical record.
- 30-day mortality, as documented in the patient medical record.
- Total post operative length of stay, (from day of surgery to the day of discharge from treating hub) as documented in the patient medical record.
- The number of days alive and out of hospital, measured at 90 days through review of the patient medical record.

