- The participant's destination on discharge from primary surgical bed. This will be derived from the patient medical record and recorded as own home/rehab facility/respite facility/residential care/nursing care.
- Contralateral limb outcomes including both minor and major amputation. This will be collected either via self-report at telephone follow up or collected from the patient medical record.

Rehabilitation outcomes

- Basic Amputee Mobility Score (BAMS): A score which can be used for daily assessment of the basic mobility of patients with leg amputation. This score will be used to assess the participants early mobility and will be measured by review of the participant's medical records at 5 days post procedure. Scores will be derived in alignment with the BAMS manual (16).
- Prosthesis assessment measured using the Special Interest Group in Amputee Medicine Score (SIGAM) (17): a single-item scale comprising six clinical grades (A-F) of amputee mobility. This score will be assessed from the review of the patient medical record at both the point of discharge from hospital and discharge from rehabilitation.
- Participant referral for prosthetic assessment, as recorded in the patient medical record it will be documented whether the participant has been referred or not.

If a participant is referred for prosthetic assessment:

- Amputee mobility predictor without prosthesis score (AMPnoPRO): an assessment tool designed to measure the functional status of lower-limb amputees without the use of a prosthesis (18). This will be recorded during the assessment of the initial visit at a prosthetic centre.
- The achieved expected level of rehabilitation. This will be the difference in score between the patients initial AMPnoPRO and final AMPnoPRO (non-prosthesis users) and AMPPro (prosthesis users) scores.

For participants issued with a prosthetic limb (to each be collected from participants remotely at 8-month intervals post randomisation):

- Trinity Amputation and prosthesis experience score (TAPES): consisting of 9 subscales which address psychosocial factors, activity restriction and satisfaction with the prosthesis (19). This score will be used to assess the participants experience of the prosthesis.
- Socket comfort score (SCS): an 11-point scale from 0-10, where 0 represents the most uncomfortable and 10, the most comfortable socket imaginable (20).
- Self-reported prosthetic wear time and usage.

Social care and long-term outcomes

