The following measures will be collected from participants remotely at 8-month intervals post randomisation)

- Participant requirement for both paid/formal care and unpaid friends and family care.
- The Adult Social Care Outcomes Toolkit (ASCOT) SCT4 questionnaire: a multi-attribute utility index designed for the evaluation of long-term social care services, comprised of eight attributes that capture aspects of social carerelated quality of life (21).
- The number of participant self-reported falls (defined as the participant falling, tripping, stumbling or making contact with the ground) and associated complications. Participants will be asked to recall this information for the previous 4 weeks.
- Activities-specific Balance Confidence (ABC) scale: a questionnaire developed to assess the balance confidence of individuals when performing daily activities, on a wide continuum of less and more challenging activities (22).
- The Reintegration to Normal Living Index (RNLI): a measure to assess the reintegration into normal social activities for those with chronic illness. The 11 items within the index are each accompanied by a VAS anchored by phrases reflecting whether the statement describes the situation of the patient (23).
- Pain and phantom pain assessment assessed using a VAS (as previously described for the procedural pain outcome).

Health economics outcomes

• Resource use: a tailored questionnaire will collect data on healthcare resource use, prosthetics, private health services, and productivity loss.

Outcomes	Timepoint					
	Baseline		Pre/Peri/P ost Procedure	Discharge	Between randomisation and FU	Follow-up
Quality of Life (EQ5D)	x					x
Falls	х					Х
Frailty assessment	х					
Pain	х		х	х		Х
Perioperative blood loss			х			
High observation/intensive care admission				x		
Within hospital complications		R A	х	x		
Wound healing		N	х	х		Х
Further amputation surgery		0	х	x		x
30-day mortality						х
Total post-operative length of stay		S				x
Number of days alive and out of hospital (at 90 days)		T I				x
Discharge destination		N		x		
Contralateral limb outcomes	x					x
BAMS					х	
SIGAM					Х	
Prosthesis referral				х		Х
AMPnoPRO					Х	
Achieved expected level of rehabilitation					x	
Prosthetic wear time and usage					x	
Use of formal and informal care						x
Resource use						x
TAPES					X	
SCS					Х	
ASCOT						х
Balance (ABC)						х
RNLI						x

Table 1: Timeline of all outcomes to be collected

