10.4 Health economic analysis

A within-trial cost-utility analysis (CUA) will be undertaken from an NHS and personal social services (PSS) perspective to assess the cost effectiveness of TKA compared to AKA in adult patients requiring MMLA but who are unsuitable for a BKA

Costs considered in this economic analysis will include intervention costs within hospitals and costs of post-surgery healthcare service use. Intervention costs will be calculated by quantifying hospital record data extracted after discharge and applying national average costs (34). Post-surgery service use costs will be calculated by collecting data using a bespoke patient self-report resource utilisation questionnaire and multiplying by unit costs obtained from national databases, such as the UK national database of National Cost Collection (34) and the Unit Costs of Health and Social Care report produced by the Personal Social Services Research Unit (35). The post-surgery service use will include residential care, primary care, hospital care, social services and wider societal costs, such as productivity and patient costs.

Effectiveness for the health economic analysis will be measured using EQ-5D-5L (13) administered at each follow up. The EQ-5D-5L results will be valued and mapped to 3L values using the approach recommended by NICE (36) to provide utility scores at multiple follow-up time points, while Quality Adjusted Life Years (QALYs) will be calculated using the area under the curve (AUC) method over the study period (37).

The primary outcome of the cost-utility analysis will be the incremental costeffectiveness ratio (ICER) to combine the estimated costs and QALYs. Rubin's multiple imputation method will be used to impute missing data (38); while regression methods will be used to control for differences in baseline utility (39) and other prognostic variables, following the approach recommended by Glick and colleagues (40). The regression coefficient on treatment will then represent the mean difference in cost and QALYs between TKA and AKA. To assess the uncertainty, a, a nonparametric bootstrap method with 5000 iterations will be used to produce confidence intervals around the cost and QALY differences. Results will be presented in the conventional form of cost-effectiveness acceptability curves (CEAC) (41) to show the probability of the intervention being cost-effective over a range of willingness-to-pay (WTP) thresholds.

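### Care use and resource use are scheduled only after randomisation and pre-admission residence is not specified, which costs precision and blurs new and existing care in secondary and economic outcomes

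*Protocol*

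**What the plan says.** Protocol section 4.3.2, under social care and long-term outcomes, opens with the schedule: "The following measures will be collected from participants remotely at 8-month intervals post randomisation". The first item under it is "Participant requirement for both paid/formal care and unpaid friends and family care". The health economics outcome is described as "Resource use: a tailored questionnaire will collect data on healthcare resource use, prosthetics, private health services, and productivity loss".

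In Table 1 the row "Use of formal and informal care" has one mark, under Follow-up, and so does the resource-use row. EQ-5D, falls, frailty, pain and contralateral limb outcomes each have a Baseline mark. Table 2 starts at month 4, so it adds no baseline point.

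A further secondary outcome is "The participant's destination on discharge from primary surgical bed", coded from the medical record in five categories from own home to nursing care. Table 1 marks it at Discharge only. No pre-admission counterpart is named in the protocol.

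Section 4.3.2 begins with a general statement: "Secondary outcomes will be collected at baseline, within the hospital 5 days post procedure". No care or resource-use item is then given a baseline point. Section 10.4 says that for costs and QALYs "regression methods will be used to control for differences in baseline utility (39) and other prognostic variables", without listing those variables.

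**The concern.** A participant who already lived in a nursing home, or already had daily care, is recorded after surgery in the same way as one who lost independence after the amputation. Section 5 sets no restriction on prior residence or prior care. It admits people with an existing below-knee amputation that needs revision, and section 6.3 anticipates an existing contralateral major amputation. Some participants can therefore be expected to have care before they enter.

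The protocol gives these outcomes weight. The background stresses the cost of formal and informal care, states that about a third of patients are discharged to a care facility, and cites return home (51% after TKA, 43% after AKA) among the registry findings in favour of TKA. Section 10.4 costs residential care and social services after surgery.

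Without a baseline value, three things are lost for these outcomes: precision from adjustment, correction of a chance imbalance in prior care, and the ability to say how much of the care seen at follow-up is new. An analysis plan written later cannot supply data that were never recorded. Asking about prior care later would rely on recall after allocation is known, because section 6.4 leaves participants and assessors unblinded.

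**Working it through.** **Reading the schedule**

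| Item | Text of 4.3.2 | Table 1 | Baseline value on the written schedule? |
|---|---|---|---|
| Formal and informal care | Every 8 months after randomisation | Follow-up | No |
| Resource use | Questionnaire, no baseline named | Follow-up | No |
| Discharge destination | From the record at discharge | Discharge | Pre-admission residence not specified |
| EQ-5D, frailty | EQ-5D at baseline; frailty is a minimisation factor (6.3) | Baseline | Yes |

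**Number per arm.** The plan's total reproduces from section 10.1 (difference 0.074, SD 0.2, 90% power, two-sided 5%, 20% loss):

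- n = 2 × (1.960 + 1.282)² × 0.2² / 0.074² = 153.5, so 154 analysed per arm.
- 154 / 0.8 = 192.5, so 193 randomised per arm and 386 in total.

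I use 193 per arm because it matches the stated total. The 183 per arm in the same section doubles to 366 and does not match; that is a separate matter.

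**Gain from a baseline covariate.** The residual variance is a fraction 1 − r² of the unadjusted variance, and the equivalent gain in sample size is 1/(1 − r²) − 1. The correlation r is assumed, since the protocol gives none.

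- r = 0.3: variance falls by 9%, equal to 1/0.91 − 1 = 10% more participants.
- r = 0.6: variance falls by 36%, equal to 1/0.64 − 1 = 56% more participants.

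This is the formula for a linear model. It suits costs or hours of care better than a five-category destination.

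**Discharge home.** Registry rates of 51% and 43%, two-sided 5%, normal approximation:

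- All participants, 193 per arm: power about 35%.
- Suppose a share q lived in care beforehand and none of them is counted as going home (both assumed). Restricting to those admitted from home gives 193(1 − q) per arm and rates of 0.51/(1 − q) and 0.43/(1 − q).
  - q = 5%: 183 per arm, 53.7% v 45.3%, power 37%.
  - q = 10%: 174 per arm, 56.7% v 47.8%, power 38%.
  - q = 15%: 164 per arm, 60.0% v 50.6%, power 41%.

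**Chance imbalance.** If a proportion p lived in a care home before admission (assumed), the 95% range of the difference between arms under simple randomisation is ±1.96 × √(2p(1 − p)/193).

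- p = 5%: ±4.3 percentage points.
- p = 10%: ±6.0 points.
- p = 20%: ±8.0 points.

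The registry difference in return home is 51 − 43 = 8 points. Minimisation on frailty and contralateral amputation should narrow these ranges to the extent that those factors predict prior residence; residence and care are not minimisation factors themselves.

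**The case against.** The strongest reply is that randomisation already deals with the important part. Prior care is balanced in expectation, so the TKA–AKA difference in care, destination or cost is unbiased without a baseline value. This stands. A reader might infer that follow-up care cannot be read as an effect of the allocated surgery, or that the comparison is biased. The documents do not support either. Existing care enters both arms alike, and no objective in section 3.2 is to estimate newly arising care after amputation.

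Second, silence is not absence. The caption "Table 1: Timeline of all outcomes to be collected" confines the table to outcomes, and section 6.4 has patient preferences recorded at baseline although they are not in it. Residence may be on an unseen baseline form. It may also be recoverable from the notes, which already supply discharge destination. So it would be wrong to say that residence is not collected, or cannot be recovered; it is not specified. The reply is weaker for care use and resource use, which do have rows, and whose rows have no Baseline mark.

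Third, some adjustment is available. Baseline EQ-5D and frailty are collected, and section 10.4 leaves room for further prognostic variables whose list belongs in the health economics plan. This stands in part: neither measure shows who already had paid or family care. A reader might also take prior care to be the strongest predictor of these outcomes. That is plausible, but the protocol gives no figure for it.

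Finally, the protocol aims to limit what it asks of participants, and baseline must be complete before a randomisation held in the week before surgery. That is a fair reason to keep any addition short, and it makes a full baseline resource-use form debatable.

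**Conclusion.** The point holds in a limited form. On the written schedule, care use and resource use have no baseline value, and pre-admission residence is not specified. Adjustment for prior care is therefore only partial, a chance imbalance in it cannot be corrected, and new care cannot be told from existing care. The damage is to precision and interpretation of secondary and economic outcomes. It does not reach the primary outcome or the validity of the randomised comparison.

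The size is uncertain. The 9% to 36% cut in variance rests wholly on assumed correlations of 0.3 to 0.6. For discharge home the gain is modest, from about 35% to 37-41% power. It also assumes that 5-15% lived in care beforehand, that none of them counts as going home, and that the registry rates apply. That outcome stays underpowered either way. The case for change is that the addition is cheap and that prior care use is hard to recover reliably once participants have been randomised.

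**What to change.** In Table 1, mark two items at baseline, or state that the baseline form already holds them:

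- usual residence before admission, in categories comparable with discharge destination;
- current paid and unpaid care.

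A very short item on prior resource use is optional. Bring the general sentence at the start of section 4.3.2, which names baseline, into line with the table rows.

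Name these items as covariates for care need, discharge destination and the cost regression in section 10.4. Report return to usual residence alongside destination.

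The cost is a few questions before randomisation, so a few minutes of extra burden for patients awaiting surgery. For anyone already randomised, residence might be sought in the medical record; prior care is less likely to be recovered reliably.

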2.0 Background and Rationale

Approximately 5,000 major lower limb amputations are performed each year in the UK (1), with numbers increasing due to the ageing population and rising prevalence of diabetes (2). Major lower limb amputation (MLLA) includes amputations conducted below the knee (BKA), above the knee (AKA) and through the knee (TKA). Costs to the NHS are approximately £200M/year (3), although this figure does not include the significant costs associated with formal and informal care, homecare visits, residential and nursing home placement. Following MLLA many patients do not return to independent living, with approximately one third of patients being discharged to a care facility (1).

Irrespective of the surgical procedure completed, MLLA has a significant impact on patient quality of life (4). A recent review concluded that the ability to walk successfully with a prosthesis following MLLA had the greatest positive impact on patient quality of life (4). AKA was negatively associated with quality of life due to increased difficulty in walking with a prosthesis (4). In addition to quality of life impacts, MLLA has substantial health implications, including anxiety, depression, altered body image and social discomfort, and the loss of general fitness and independence, which will contribute further to patient burden and healthcare costs (4, 5).

Patients not suitable for a BKA are usually offered an AKA, and less commonly a TKA. There are clear theoretical advantages from a longer residual limb which can be achieved with TKA, with end weight bearing capacity for rehabilitation and biomechanical advantage. However, there is little robust evidence to compare clinical and rehabilitation outcomes and complication rates of TKA and AKA (6). Where evidence is available, this is in the form of observational studies (3, 7) which have included small numbers of participants undergoing TKA compared to AKA and have failed to differentiate between AKA and TKA or between variations of TKA (3, 7). The heterogeneity of the available studies has resulted in variability in rates of uncomplicated healing, reoperation, successful ambulation, and survival but

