6.4 Blinding

The operating surgeon will be informed of the allocation and will not be blind to the intervention. Due to the nature of the intervention, blinding of participants and assessors is not possible. Data on patient preferences will be collected at baseline.

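### The falls outcome also counts trips and stumbles that do not end on the ground, so a difference in falls between arms can be diluted, or reversed if near-falls are commoner after TKA

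*Protocol*

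**What the plan says.** Under the social care and long-term outcomes in Protocol section 4.3.2, the outcome is "The number of participant self-reported falls", "defined as the participant falling, tripping, stumbling or making contact with the ground", together with associated complications. The recall period is short: "Participants will be asked to recall this information for the previous 4 weeks". The schedule is "The following measures will be collected from participants remotely at 8-month intervals post randomisation", which Table 2 sets out for falls as months 8, 16 and 24. Table 1 adds a baseline assessment. The section describes no separate count of trips or stumbles without a fall, and no denominator for walking or prosthesis use.

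Three other places bear on interpretation:

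- Section 2.0 cites a review in which "AKA was negatively associated with quality of life due to increased difficulty in walking with a prosthesis", and credits TKA with "end weight bearing capacity for rehabilitation and biomechanical advantage".
- Section 4.3.2 lists "Self-reported prosthetic wear time and usage", but only for participants issued with a limb and with no link to the falls count.
- Section 6.4 says that "blinding of participants and assessors is not possible", so participants report their own count knowing their allocation.

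**The concern.** The four terms are alternatives. Falling and reaching the ground are listed beside tripping and stumbling, so a stumble that is recovered meets the definition. An outcome named falls therefore adds two kinds of event that need not move together. Near-falls depend partly on how much a person is on their feet. If one arm is more active, its count can rise for a reason that is not harm.

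At stake is the reading of one secondary outcome. A true difference in falls could look smaller than it is, or point the wrong way, and a reader could not tell whether the difference came from falls or from recovered stumbles. Near-falls are also more subjective to recall than ending up on the ground, which matters when participants are unblinded.

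**Working it through.** The protocol gives no figure for falls, so there is nothing to reproduce. The arithmetic below is illustrative, and every rate in it is assumed.

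**Main calculation.** Let the AKA arm have true fall rate f and k near-falls per fall. Let R be the true falls ratio (TKA to AKA) and m the near-fall ratio (TKA to AKA).

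- Recorded rate, AKA: f(1 + k)
- Recorded rate, TKA: f(R + mk)
- Recorded ratio: (R + mk) / (1 + k)

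With R = 0.70:

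| m | k = 1 | k = 3 |
|---|---|---|
| 0.7 | (0.70 + 0.70)/2 = 0.70 | (0.70 + 2.10)/4 = 0.70 |
| 0.8 | (0.70 + 0.80)/2 = 0.75 | (0.70 + 2.40)/4 = 0.775 |
| 1.0 | (0.70 + 1.00)/2 = 0.85 | (0.70 + 3.00)/4 = 0.925 |
| 1.2 | (0.70 + 1.20)/2 = 0.95 | (0.70 + 3.60)/4 = 1.075 |

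There is no distortion when near-falls fall by the same proportion as falls (m = R). For m between 0.70 and the reversal point, the effect is diluted. Reversal needs R + mk > 1 + k, that is m > 1 + 0.30/k: above 1.30 for k = 1 and above 1.10 for k = 3.

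**Cross-check with a different model.** Recorded rate = true falls + share walking × trips or stumbles per walker, s. Assume true falls per four weeks of 0.30 (AKA) and 0.20 (TKA), a true ratio of 0.67.

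- 30% walking in both arms, s = 1: (0.20 + 0.30)/(0.30 + 0.30) = 0.50/0.60 = 0.83. Diluted.
- 30% against 35% walking, s = 2: (0.20 + 0.70)/(0.30 + 0.60) = 0.90/0.90 = 1.00. Hidden.
- 30% against 35% walking, s = 4: (0.20 + 1.40)/(0.30 + 1.20) = 1.60/1.50 = 1.07. Reversed.

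This model gives both arms the same s, so it cannot show the benign case in which TKA reduces stumbles per walker. The table above can.

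**Does anything else in the protocol separate the events?** Sections 9.1 and 9.2 confine adverse events to the stump, the index surgery or intervention on the residual limb, and Table 3 does not list falls. Associated complications would pick out injurious events but would not tell an uninjured fall from a stumble. SIGAM, TAPES, wear time and the ABC scale describe mobility and confidence. They help to interpret a difference but do not split the count.

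**The case against.** The strongest reply is that this is a low-stakes choice and possibly a deliberate one. A broad count of instability that includes near-falls is a legitimate measure. The outcome plays no part in the sample size, the primary analysis or the pilot progression criteria. Changing the wording after collection has begun would create two definitions. Much of this stands, and it sets the priority. It does not remove the mismatch between the outcome's name and what it counts.

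Several stronger readings are tempting, and the protocol does not support them:

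- *The trial collects only one combined number, so the information is lost.* The questionnaire is not shown. Section 4.3.2 describes an outcome, not the form, which may already ask about event types separately.
- *The trial expects TKA patients to walk more, so a reversal is likely.* Section 2.0 speaks of theoretical advantages and little robust evidence. Section 11.1 says only that a functional benefit may occur and cannot be guaranteed. The sentence on AKA and walking difficulty comes from a review of major amputation and does not name TKA as the comparator. A longer, end-bearing limb could also reduce stumbles, which is why values of m below 1 belong in the table.
- *The definition alone makes the count track activity.* True falls also depend on how much people walk. A ground-contact definition weakens that link without removing it.
- *Falls are a safety endpoint.* The protocol lists them with social care and long-term outcomes and handles safety in section 9.

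**Conclusion.** The point holds as a cheap, low-priority improvement. As worded, the definition counts recovered trips and stumbles as falls, and no other section corrects this. For an assumed true falls ratio of 0.70 with 1 or 3 near-falls per fall, the recorded ratio runs from 0.70 (no distortion, m = 0.7) to 0.95 or 1.08 (m = 1.2). Dilution is the ordinary result when near-falls are equal between arms. Reversal requires more near-falls after TKA, which is possible if those patients are more active but is not shown by anything in the protocol. The values of R, k and m are all assumptions, so the actual size cannot be computed from the document.

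A statistical analysis plan could adjust for exposure. It could not separate events that the form records as one count, so the definition has to be settled in the protocol and the questionnaire.

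**What to change.** First check the questionnaire. If it already separates the events, align the wording of section 4.3.2 with it. If not, ask for two counts at baseline and at months 8, 16 and 24:

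- (a) falls, meaning events that ended with the participant on the ground or a lower level;
- (b) trips or stumbles recovered without a fall.

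Make (a) the falls outcome and report (b) separately. Also report (a) + (b), which approximately rebuilds the present count and keeps continuity with data collected under the current definition.

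The cost is one reworded and one added question at four time points, and slightly more burden on participants. Data already collected as a single count stay pooled, so the change is worth more the sooner it is made.
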